1 INTRODUCTION

The purpose of this Statistical Analysis Plan (SAP) is to provide detailed descriptions of the statistical methods, data derivations and data displays for study protocol XPF-009-302 Version 3.0, "An open-label extension study of XEN496 in pediatric subjects with KCNQ2 developmental and epileptic encephalopathy" dated 09 May 2022 for final analysis. The table of contents and templates for the tables, figures and listings (TFLs) will be produced in a separate document.

Any deviations from this SAP will be described and justified in the Clinical Study Report (CSR).

The preparation of this SAP has been based on International Conference on Harmonization (ICH) E3 and E9 guidelines.

2

examinations,

Objectives Endpoints **Primary** To assess the long-term safety and Severity and frequency of adverse • tolerability of XEN496 in pediatric subjects events (AEs) and serious adverse with KCNQ2 developmental and epileptic events (SAEs); clinically significant encephalopathy (KCNQ2-DEE) who had changes in laboratory tests, vital signs, electrocardiograms (ECGs), physical participated in the primary study (XPF-009neurologic 301). and CI

STUDY OBJECTIVES AND ENDPOINTS

Secondary

Secondary	
To evaluate the intra-subject efficacy of XEN496 in reducing seizure frequency compared to prior placebo treatment in pediatric subjects with KCNQ2-DEE who were previously randomized to receive placebo in the primary double-blind Phase 3 study (XPF-009-301).	• Change in monthly countable motor seizure frequency, comparing the first 15 weeks of XEN496 treatment in the open label extension (OLE) study to the seizure frequency reported during treatment in the preceding primary study (XPF-009-301), among only those subjects who were randomized to the placebo arm in the primary study (XPF-009-301). (key efficacy endpoint)
To assess the long-term effect of XEN496 on seizure reduction in pediatric subjects treated with XEN496.	 Change from pre-randomization baseline in the previous study over time based on response categories (<25%, 25 to <50%, 50 to <75%, 75 to <100%, 100%), based on estimated seizure frequency every 3 months during the OLE period. Percent change from baseline in countable motor seizure frequency, relative to pre-randomization baseline of the previous study (XPF-009-301), assessed over time every 3 months during the OLE.

Statistical Analysis Plan

Objectives	Endpoints			
	• Percent change from baseline in countable motor seizure frequency, relative to pre-randomization baseline of the previous study (XPF-009-301), for every 3 months based on combined data from both XPF-009-301 and the OLE, by the treatment group in the previous study.			
To evaluate Caregiver Global Impression of Severity (CaGI-S) and Caregiver Global Impression of Change (CaGI-C) scores in pediatric subjects with KCNQ2-DEE.	 Change over time in CaGI-S scores for the subject's seizures and overall condition. Change over time in CaGI-C scores for the subject in the following domains: overall condition, seizures, behavior, alertness, motor skills, visual function, and communication. 			
To assess neurocognitive development and behavior after dosing with XEN496 in pediatric subjects with KCNQ2-DEE.	 Change over time in neurocognitive development based on the Bayley Scales of Infant and Toddler Development, Third Edition (BSID-III). Change over time in adaptive behavior based on the Adaptive Behavior Assessment System, Third Edition (ABAS-3). 			
To evaluate the investigator's global impression of the change in the subject's overall condition, assessed using the Clinical Global Impression of Change (CGI-C) scale.	• Change over time in CGI-C scores for the subject's seizures and overall condition.			
To evaluate the use of rescue medication and change in background antiseizure medications (ASMs).	 Use of rescue medication. Use of concomitant medications and treatments used for seizure control. 			
To assess the impact of XEN496 on the	• Change in quality of life of subjects			

Version: Final 1.0 Date: 04MAY2023 Page 10 of 47 CCI

Statistical Analysis Plan

Objectives	Endpoints
quality of life of caregivers and subjects with KCNQ2-DEE.	 with KCNQ2-DEE, based on the Pediatric Quality of Life Inventory (PedsQL). Change in quality of life of subjects with KCNQ2-DEE, based on the Pediatric Quality of Life Inventory, Family Impact Module (PedsQL-FIM).
To evaluate the plasma concentrations of ezogabine and N-acetyl metabolite of retigabine (ezogabine) (NAMR).	• Plasma concentrations of ezogabine and NAMR (for subjects treated in the OLE study only).

3 STUDY DESIGN

3.1 General study design

This is a Phase 3, open-label, long-term extension study to evaluate the safety, tolerability, and efficacy of XEN496 administered as adjunctive therapy in pediatric subjects with KCNQ2-DEE who participated in the primary study, XPF-009-301.

Approximately 40 subjects may be included in the study based on the anticipated number of subjects who could roll over from Study XPF-009-301.

Subjects will undergo the following:

- Screening/Baseline period Subjects will undergo eligibility assessment at Visit 22 or early termination in the primary study (XPF-009-301).
- Treatment period 36 months:
 - Blinded transition/titration period
 - Open-label period approximately 35 months.

Subjects who received XEN496 in the primary study will continue to receive XEN496 at the same dose throughout the OLE.

[figure not shown]
Subjects allocated to placebo in the primary study will be required to begin a titration of XEN496 CCI

- CCI
- Taper period CCI
 Subjects who discontinue or complete the study treatment will be required to taper off study drug CCI
 The actual duration of the taper period will depend on the subject's dosage prior to taper.
 - Follow-up Approximately 4 weeks after subjects have tapered off of study drug.

Total study duration per subject is estimated to be 37 months.

The Study Design Schematic is presented in Figure 1.

Figure 1: Study Design Schematic

3.2 Randomization and blinding

[figure not shown]
This is an open label study and randomization is not applicable.

A double-blind transition/titration period will be used to maintain blinding to the treatment allocation in the primary study (XPF-009-301). During this period, treatment will be administered under double-blind conditions: Subjects and their caregivers, the investigators, and the outcomes assessor will be blinded to treatment assignment.

3.3 Study treatments and assessments

[figure not shown]
Total treatment duration per subject is estimated to be 36 months.

The treatment period begins with a dose transition/titration period. Subjects who received XEN496 in the preceding study will continue to receive XEN496 at the same dose, in a blinded manner, without any further titration.

Statistical Analysis Plan Protocol Number: XPF-009-302

Version: Final 1.0 Date: 04MAY2023 Page 13 of 47

The optimally-tolerated dose level established during the transition/titration period will be maintained throughout the duration of the open-label period unless dose adjustment is required.

A detailed description of procedures and assessments to be conducted during this study is summarized in the Scheduled of Study Assessments in Table 2 and Table 3 below.

DCON

Statistical Analysis Plan (SAP)

R XENON

Table 2: Schedule of Activities, Baseline and Treatment Period Up to 1 Year

Protocol Number: XPF-009-302

Version: Final 1.0 Date: 04MAY2023 Page 16 of 47

Protocol Number: XPF-009-302

[figure not shown]

Statistical Analysis Plan (SAP)

R XENON

C

R XENON

[figure not shown]

Protocol Number: XPF-009-302 Statistical Analysis Plan

Page 17 of 47

Page 18 of 47 Version: Final 1.0 Date: 04MAY2023

Protocol Number: XPF-009-302 Statistical Analysis Plan

[figure not shown]
Statistical Analysis Plan (SAP)

R XENON

C

Statistical Analysis Plan (SAP)

Table 3: Schedule of Activities, Long-term Treatment Period (up to 3 Years), and Taper and Follow-up Visits

Protocol Number: XPF-009-302

DocUUID : 33115ccb-9ab0-4f4a-bf62-222e09e4c4d6

Version: Final 1.0 Date: 04MAY2023 Page 20 of 47

Statistical Analysis Plan Protocol Number: XPF-009-302

K XENON

Statistical Analysis Plan (SAP)

CCI

R XENON

Cl	

Statistical Analysis Plan Protocol Number: XPF-009-302

Version: Final 1.0 Date: 04MAY2023 Page 21 of 47

Version: Final 1.0 Date: 04MAY2023 Page 22 of 47

Statistical Analysis Plan Protocol Number: XPF-009-302

[figure not shown]
Statistical Analysis Plan (SAP)

H XENON

4 SAMPLE SIZE DETERMINATION

No formal sample size calculation has been performed. Only those subjects who have completed the previous study, XPF-009-301, are eligible to be enrolled into this study. Therefore, the expected total sample size will be up to approximately 40 subjects.

5 ANALYSIS POPULATIONS

5.1 Enrolled Set

Enrolled set include all subjects who signed the informed consent form.

5.2 Safety Set

[figure not shown]
CCI

5.3 Key Efficacy Analysis Set

The key efficacy analysis set includes those subjects who were treated with placebo in the preceding primary study (XPF-009-301) and switched to XEN496 treatment in the current study, with at least 4 weeks of evaluable seizure data in both study periods.

5.4 Secondary Efficacy Analysis Set

The secondary efficacy analysis set includes those subjects who were treated in both the preceding primary study (XPF-009-301) and the current OLE study, with at least 1 evaluable seizure data in both study periods.

6 STATISTICAL CONSIDERATIONS AND ANALYSIS

6.1 Derived Variables

The Table 4 provide the list of derived variables for demographic and baseline characteristics, various duration derivations, drug compliance, baseline derivations and other important derivations applicable for this study. Derived efficacy variables will be provided in Section 6.1.1

Table 4 Derived variables

Variables	Formula			
Demographic and Basel	Demographic and Baseline characteristics			
Age (in months)	integer ((Date of informed consent – Date of birth + 1)/ 30.4375)			
Age (in years)	integer ((Date of informed consent – Date of birth + 1)/ 365.25)			
OLE Baseline	Last non-missing value prior to start of study drug in OLE period i.e, Data collected at visit 22 or early termination (ET) visit in the primary study (XPF-009-301) will be considered. If any unscheduled non-missing value available after visit 22 or ET and before first dose in OLE, unscheduled visit value will be considered as baseline.			
Double blind Baseline	Last non-missing value prior to start of study drug in XPF-009- 301 study			
Derivation of Duration				
Study day at any visit	Date of interest – date of first dose of study drug in OLE +1, if date of measurement is on or after the first OLE dose date, or Date of measurement – first dose date, if date of measurement is prior to the first dose date. No Study Day 0 is defined			
Extent of Exposure (Days)	Date of last study medication intake in OLE – Date of first study medication intake in OLE + 1			
Extent of Exposure (Weeks)	Extent of exposure (days)/7			

[figure not shown]
For the computation of Bayley scores, age will need to be expressed in years, months, and days. The following algorithm can be used to derive these values:

TOTDAYS = ADT – BIRTHDT; AGEYRS = FLOOR (TOTDAYS / 365.25); /* age in years */

[figure not shown]

REMAINDR = TOTDAYS – (365.25*AGEYRS); AGEMTHS = FLOOR(REMAINDR / 30.4375); /* age in months */ AGEDAYS = ROUND(REMAINDR – (30.4375*AGEMTHS)); /* in days */

Visit windows for vitals, ECG, and labs are specified in the Table 5. If there is more than one observation within a visit window, the value closest to the nominal study day will be used. If two values are equidistant from the nominal study day, the later value will be used.

Version: Final 1.0 Date: 04MAY2023 Page 26 of 47

6.1.1 Efficacy Variables

6.1.1.1 Seizure frequency

Caregivers will record all countable motor seizures in the daily seizure diary, which will be reviewed at selected visits as specified in Table 2 and Table 3. The following motor seizures with a duration of at least 3 seconds will be recorded in the seizure diary:

[figure not shown]
- Focal tonic.
- Focal motor.
- Focal with secondary generalization.
- Generalized tonic.
- Focal clonic.
- Generalized clonic.
- Generalized tonic-clonic.

[figure not shown]
Important exclusions to the countable seizures are:

- Single myoclonic jerks.
- Staring spells without a motor component.

If epileptic spasms are suspected or reported, the investigator must be contacted immediately to confirm the diagnosis and to initiate treatment.

The denominator will be based on those evaluable days when an entry of yes or no is provided on occurrence of seizure of any type. Days with counts of 0 seizure will be included in the denominator; while days with missing seizure counts will be excluded from the denominator.

The average monthly seizure frequency (per 28 days) will be derived with the formula below:

sum of daily countable seizure counts reported during the placebo (or XEN496) treatment period

Total number of days within the time period when seizure data is reported $\times 28$

Percent change of average monthly seizure frequency will be derived using the below formula where *average monthly seizure frequency* is defined as above and *Baseline* refers to the comparator period appropriate for the endpoint (eg. placebo period for the key efficacy endpoint and the pre-randomization baseline period for other efficacy endpoints):

Average monthly seizure frequency – Baseline average monthly seizure frequency Baseline average monthly seizure frequency × 100

6.2 Handling of missing data and outliers

6.2.1 Missing data analysis methods

The key efficacy endpoint of seizure frequency will be derived from the days with nonmissing seizure data as described in Section 6.1.1. To assess the impact of missing data due to early dropout, sensitivity analysis incorporating missing data multiple imputations with both missing at random (MAR) and missing not at random (MNAR) mechanisms. Details of the analysis will be specified in the analysis section 7.6.1..

6.2.2 Handling of missing or incomplete dates

Missing or partial AE onset dates and times will be imputed so that if the partial AE onset date/time information does not indicate that the AE started prior to treatment or after the treatment emergent adverse event (TEAE) period, the AE will be classified as treatment-emergent. These data imputations are for categorization purpose only and will not be used in listings. No imputation is planned for date/time of AE resolution.

No imputation for medication start/end dates or times will be performed. Partial dates will be used to determine whether concomitantly. If a medication date or time is missing or partially missing date cannot be determined whether it was taken concomitantly, those medications will be considered as concomitant medication.

Imputation rules for missing or partial AE start date are defined below:

- 1) If only Day of AE start date is missing:
 - If the AE start year and month are the same as that for the OLE first dose date, then impute the AE start day as the day of OLE first dose date, if the full (or partial) AE end date is NOT before the first dose date or AE end date is missing: otherwise, impute the AE start day as 1.
 - Otherwise, impute the AE start day as 1.

- 2) If Day and Month of AE start date are missing:
 - If AE start year is equal to first dose year, then impute the AE start Month and Day as the Month and Day of OLE first dose date, if the full (or partial) AE end date is NOT not before the first dose date or AE end date is missing; otherwise, impute the AE start Month as January and the Day as 1.
- 3) If AE start date is missing:
 - If the AE start date is completely missing, then query site with no imputation.
 - Also compare the full (or partial) AE end date to the first dose date. If the AE end date is before the first OLE dose date, then the AE should be considered as a pre OLE treatment AE.
 - Otherwise, the AE will be considered as TEAE.

Compare the imputed AE start date with TE period to determine whether the AE is pre OLE treatment AE or TEAE.

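### A doubled negative in the SAP's rule for year-only AE onsets, taken literally, reverses the end-date test that rule 1 applies

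*SAP*

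**What the plan says.** SAP 6.2.2 opens with an aim: a partial onset date is imputed so that an AE counts as treatment-emergent when the onset information "does not indicate that the AE started prior to treatment" and does not place it after the treatment-emergent period. Three rules follow.

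- **Rule 1 (day missing).** If the onset month and year are those of first OLE dose, the first-dose day is used "if the full (or partial) AE end date is NOT before the first dose date or AE end date is missing". Otherwise the day is set to 1.
- **Rule 2 (day and month missing).** When the onset falls in the year of first OLE dose, the onset takes that dose's month and day "if the full (or partial) AE end date is NOT not before the first dose date"; a missing end date leads to the same imputation. The fallback is "otherwise, impute the AE start Month as January and the Day as 1".
- **Rule 3 (onset wholly missing).** "If the AE end date is before the first OLE dose date, then the AE should be considered as a pre OLE treatment AE". Otherwise it is a TEAE.

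The section ends by comparing the imputed onset with the treatment-emergent period, which decides whether the AE is pre-OLE or a TEAE. It also says that imputed dates serve categorisation only and stay out of the listings, and that AE resolution dates are not imputed.

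**The concern.** Rules 1 and 2 are built alike, but rule 2 carries an extra negative, which turns its condition round. Read literally, an AE that was over before the child's first OLE dose is given an onset on the dose date, and an AE that ended during treatment is sent back to 1 January.

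This is working text that a programmer would code. Long-term safety is the primary objective, and its endpoint is the severity and frequency of AEs and SAEs (SAP section 2). Subjects roll over from a preceding study, so the line between pre-OLE and on-treatment events matters. A literal program could take possible on-treatment events out of TEAE counts and add events that cannot be treatment-emergent.

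**Working it through.** The plan gives no figure to reproduce, so the check is of logic, followed by an illustrative enumeration.

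**Conditions.** Let B mean that the AE end date is before the first OLE dose date.

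- Rule 1 uses the first-dose date if (not B) or the end date is missing.
- Rule 2 as written uses it if not(not B) or the end date is missing. Since not(not B) = B, the test is: B or end date missing.

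**Branches of rule 2.** Assumptions: first dose on 15 June; onset year equal to first-dose year; an AE is a TEAE if its imputed onset is on or after first OLE dose.

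| AE end date | Onset, rule 2 as written | Class | Onset, single negative as in rule 1 | Class |
|---|---|---|---|---|
| 16 May (before dose) | 15 June, after the AE ended | TEAE | 1 January | pre-OLE |
| 15 June (dose date) | 1 January | pre-OLE | 15 June | TEAE |
| 15 July (after dose) | 1 January | pre-OLE | 15 June | TEAE |
| missing | 15 June | TEAE | 15 June | TEAE |

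For comparable end dates the two versions always disagree. For a missing end date they agree. If first dose was on 1 January, both give 1 January and the difference disappears.

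**Against the rest of 6.2.2.** The single-negative column agrees with rule 3, where only an end before first OLE dose makes an AE pre-OLE. It also agrees with the opening aim, because a bare year equal to the first-dose year does not by itself show a start before treatment. The literal column agrees with neither.

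**Enumeration.** Every onset day of a 365-day year was combined with assumed AE durations of 0, 3, 7, 14 and 30 days, with end dates known. That gives 365 × 5 = 1,825 events for each assumed first-dose date.

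| First dose | True onset on or after dose: TEAE as written | Same, single negative | Ended before dose: TEAE as written | Same, single negative |
|---|---|---|---|---|
| 1 April | 0 of 1,375 | 1,375 of 1,375 | 396 of 396 | 0 of 396 |
| 15 June | 0 of 1,000 | 1,000 of 1,000 | 771 of 771 | 0 of 771 |
| 1 October | 0 of 460 | 460 of 460 | 1,311 of 1,311 | 0 of 1,311 |

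Each row covers 1,771 events (for 15 June, 1,000 + 771). The other 1,825 − 1,771 = 54 began before first dose and ended on or after it. The literal rule calls these pre-OLE, which is true of their actual onset; the single negative calls them TEAEs, which is the conservative default. The enumeration shows direction only and says nothing about how often such records occur.

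**Size for one subject.** 1/40 = 2.5 percentage points of an overall incidence, if the subject has no other TEAE in that table row. Denominators by prior treatment group are smaller, so the shift there would be larger.

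**The case against.** The best reply is that this is a slip of the pen and not a method. The opening aim, rule 1 and rule 3 all show what was meant, and the literal rule produces onsets later than the AE's own end, which a careful programmer would probably notice. That stands, and it limits the weight of the point. It does not make the sentence correct. SAP section 1 requires deviations from the SAP to be described and justified in the study report, so a programmer who follows the evident intent departs from the written rule. Keeping imputed dates out of the listings also means that the impossible onsets would not be seen there, although the recorded dates would.

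A reader might infer more than the documents support:

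- **That every AE with a year-only onset is misclassified.** Events that straddle first dose are called pre-OLE by the literal rule, and they did begin before dosing. Missing end dates are handled as intended. An end date known only to the first-dose year cannot be placed before or after dosing, so its outcome is unclear. The error is a departure from the SAP's own conservative rule, not from true onset in every case.
- **That the safety tables will be wrong.** The visible text contains neither the definition of the treatment-emergent period nor the AE table specifications, and SAP section 2 words the endpoint as AEs and SAEs. A period starting at first OLE dose is an assumption, though it fits rule 3.
- **That rule 2 also errs by having no branch for other onset years.** No classification is shown to change. An earlier year already shows a pre-treatment start, and for a later year the opening aim gives TEAE unless the event falls after the treatment-emergent period.

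**Conclusion.** The point holds as a wording error in an operative rule. For AEs with onset known only to the first-dose year and an end date that can be compared with first OLE dose, rule 2 as written applies the opposite of rule 1's test. If the treatment-emergent period begins at first OLE dose, AEs that ended before dosing become TEAEs, and AEs that ended on or after dosing become pre-OLE, except when first dose was on 1 January. The documents do not say how many such AEs there are. The number is probably small, so no effect on TEAE incidence can be estimated beyond the single-subject figure. Nothing suggests that the reversal was intended. It should be corrected because the text, if followed, gives the wrong class.

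**What to change.** In SAP 6.2.2, rule 2, delete the second, lower-case negative so that the condition reads as in rule 1: "if the full (or partial) AE end date is NOT before the first dose date or AE end date is missing". Then confirm that the program derives rule 2 with the single negative. The cost is one word in the SAP and a check of one derivation; no data collection or protocol change is involved. A line stating what to do when the onset year differs from the first-dose year would be optional tidying, to parallel rule 1, and is not needed to correct this error.
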